#### ***10.4.2.3. Time to first response***

The time to first response will be described in the ITT population. No formal statistical comparisons are planned.

#### ***10.4.2.4. Time to treatment failure***

The time to treatment failure will be described in the ITT population. No formal statistical comparisons are planned.

### 10.4.3. Subgroups analyses

Following the protocol amendment 11, no subgroup analysis of Overall Survival, Progression-Free Survival, DCR and ORR will be performed.

## 11. SAFETY ANALYSES

Safety analysis will be performed on the safety evaluable population described in section 7.4 for each treatment arm.

### 11.1. OVERVIEW OF THE SAFETY

The adverse events incidence, overall and per CTCAE grade, will be presented. The worst CTCAE grades or maximum severity grades (for non haematological adverse events not classified by the CTCAE) will be analysed by patient, and by treatment arm, regardless or not to the relationship to treatment.

For definition of evaluable patient for non-haematological and evaluable cycle/patient for haematological and biochemical toxicity, see § 5.1, § 5.3 and §5.4, respectively.

### 11.2. ADVERSE EVENTS

#### 11.2.1. All adverse events

The incidences of the treatment-emergent adverse events (TEAE) as defined in 5.1, graded according to CTCAE version 3.0 will be presented using the MedDRA SOC and PT defined during the MedDRA coding process.

A summary table will provide by treatment arm the following:

On treatment deaths

Patients with at least one AE

Patients with at least one TEAE

Patients with at least one SAE

Patients with at least one related TEAE

Patients with at least one related TESAE

Patients with at least one TEAE leading to discontinuation

Patients with at least one TEAE requiring dose interruption and/or adjustment

Patients with at least one TEAE requiring dose interruption

Patients with at least one TEAE requiring dose adjustment

Patients with at least one TEAE requiring additional therapy

Cycles with at least one AE

Cycles with at least one TEAE

For all these items, the overall incidence, the incidence of grade 3/4, the incidence of grade 5 and the incidence of grade NA will be provided.

Overall incidences per patient will be depicted as well as the incidence of non related and related toxicities only. An analysis will also present the CTCAE grade presented for each SOC and PT per patient according to the relationship with study treatment.

Of note, some laboratory toxicities will be presented in the non-haematological adverse event tables when reported as adverse events as per study completion guidelines. However, biochemical and haematological event should be interpreted from the tables described in section 5.1

### **11.2.2. Selected adverse events**

The worst CTCAE grade per patient of Adverse Events Of Special Interest (AEOSI) listed in section 5.1. will be presented for patients treated in both arms and regarding the relationship to treatment.

### **11.2.3. Serious adverse events**

The number of patients with at least one SAE, one related (suspected and insufficiently documented) SAE, number of SAEs, number of related SAEs will be tabulated. Incidences of SAEs by SOC and PT will be presented according to the relationship with study treatment.

A listing of the serious toxicities will also be provided with the following variables: patient number, cycle number, seriousness, CTCAE grade, relationship to treatment, date of onset, date ceased and significant consequences.

### **11.2.4. Deaths**

The number and percent of patients dead will be tabulated by treatment arm, including number and percent of dead related to AE/SAE, due to progression or other reasons.

Two listings will be provided depicting the patients who died:

- patients who died within 30 days after the last administration,
- patients who died more than 30 days after the last administration.

These listings will contain the following variables: patient number, cycle number, date of death, reason of death, source of information.

## 11.3. LABORATORY TESTS

### 11.3.1. Haematological toxicities

Leukocytes, ANC, haemoglobin and platelets data will be analysed for haematological toxicity.

A first analysis will present the worst grade by patient and the worst grade experienced during a cycle. Cycles where a grade 3/4 haematological toxicity occurred will be listed by patient number. In a second analysis, the worst grade of patients according to the grade at baseline will be tabulated.

### 11.3.2. Biochemical toxicities

Liver, renal and metabolic function tests will be analysed with a focus on bilirubin, alkaline phosphatase, SGOT/AST and SGPT/ALT, creatinine, creatinine clearance, sodium, potassium and calcium.

In order to examine the evolution of biochemical toxicities, worst CTCAE grade (hypo and hyper for metabolic function tests) will be analysed in relation to the grade presented by the patient at baseline. Cycles where grade 3/4 biochemical toxicity occurred will be listed by patient number.

In addition, the relationship between liver involvement at baseline and the worst CTCAE grade during study will be studied for SGOT and SGPT. The same analysis will be done for the worst CTCAE grade of alkaline phosphatase and liver and/or bone metastases at baseline.

## 12. OTHER ANALYSES

### 12.1. HEALTH-RELATED QUALITY OF LIFE ANALYSES

The analysis of health-related quality of life will be done for each questionnaire (EORTC QLQ-C30 and QLQ-Head and Neck 35 EORTC module) on each evaluable population.

#### 12.1.1. Evaluable questionnaire

To be evaluable for health-related quality of life assessment, patients should have completed one questionnaire (at least two thirds of the questions) within seven days prior to randomisation, and at least one questionnaire (at least two thirds of the questions) during the study period. To be considered evaluable, the questionnaires should be available in the native language of the patient, otherwise, the patient will not be evaluable for quality of life. For definition of evaluable population for QOL, see § 5.1.

At baseline, only questionnaires which were completed within the window of seven days prior to the day of randomisation (and including any questionnaire filled that day) will be considered. The end of study questionnaire needs to be filled in within 30 days after the last administration in order to be evaluable. Any later questionnaire will not be analysed.

If more than one questionnaire is available within an evaluation period the last non-missing questionnaire will be analysed.

### 12.1.2. Descriptive analyses

The number of QoL questionnaires completed and evaluable per evaluation will also be given.

The quality of life will be assessed (using the EORTC questionnaires, without any medical staff influence) at baseline before randomisation, every 6 weeks during the study and at the end of treatment evaluation (within 30 days of the last dose administration).

Missing data is a typical problem of QoL analysis. There are two levels of missing data :

- Missing item(s) in a questionnaire filled in by the patient,
- Completely missing questionnaire at a given evaluation.

For the first level, if more than one third of the items is missing then the questionnaire is non-evaluable.

Each parameter will be described at baseline. Changes of the scores from baseline of the parameters (15 for QLQ-C30 and 13 for QLQ-H&N 35) will be provided for each (mean, standard deviation, median, Q1, Q3, minimum and maximum).

## 13. CHANGES INTERFERED SINCE LAST VERSION

According to the protocol amendment PA11 (05/02/2016) and the associated protocol version 7 (05/02/2016), the statistical analysis was reduced to:

- Description of study, patients and disease characteristics,
- Efficacy: analysis of the primary efficacy variable (OS) and the secondary efficacy endpoint on the ITT population only (no other efficacy population will be defined),
- Safety: exhaustive description of safety parameters.
- Other: description of Quality of Life.

Therefore, in order to perform an abbreviated Clinical Study Report (CSR), in comparison to the previous version of the SAP (version 3 dated 28/05/2014), the following analyses have been deleted:

- Analysis of primary and secondary efficacy criteria on other population than ITT,
- Analysis of efficacy criteria on subgroups of patients,
- Multivariate analyses of efficacy criteria,
- Description over time of values and changes from baseline for laboratory date, because CTCAE grades will be provided,
- Some detailed tables of disease history, prior therapies and concomitant medications, limiting the analyses to an overview of the safety and patients and disease characteristics,
- Other analyses including clinical benefit, further anti-cancer therapy, pharmacoeconomic analyses.

Summary tables of adverse events, prior therapies for SCCHN and exposure have been added.

All data will be provided in individual data listings in appendix 16.2 of the Clinical Study Report.

## 15. APPENDICES

**Appendix 1: LIST OF TABLES, LISTINGS AND FIGURES**

**Appendix 2: STATISTICAL ANALYSIS CONVENTIONS**

**Appendix 3: ADVERSE EVENTS OF SPECIAL INTEREST**

**Appendix 4: ANALYSIS OF TUMOUR LOCATION AT BASELINE**

## 15.1. APPENDIX 1: LIST OF TABLES, FIGURES AND LISTINGS

SECTION	Title	RTF reference
10.1	Number of Patients enrolled, randomized, treated and evaluable for Quality of Life [All patients]	10_1a.RTF
10.1	Patient disposition [ITT]	10_1b.RTF
10.1	Patients with at least one Protocol deviations by type [ITT]	10_1c.RTF
11.2	Demographic data [ITT]	11_2_1.RTF
11.2	Stratification factors [ITT]	11_2_2.RTF
11.2	Disease History[ITT]	11_2_3.RTF
11.2	Summary of Prior therapies for SCCHN [ITT]	11_2_6.RTF
11.2	Prior therapies: chemotherapy [ITT]	11_2_7.RTF
11.2	Prior therapies: radiotherapy [ITT]	11_2_8.RTF
11.2	Prior therapies: surgeries by SOC and PT [ITT]	11_2_9.RTF
11.2	Prior therapies: Other therapies [ITT]	11_2_10.RTF
11.2	Clinical examinations at baseline [ITT]	11_2_11.RTF
11.2	Haematological CTCAE grades at study entry [ITT]	11_2_12.RTF
11.2	Biochemical CTCAE grades at study entry [ITT]	11_2_13.RTF
11.4.1.1	Overall Survival (OS-months) [ITT]	11_4_1_1.RTF
11.4.1.1	Overall Survival (OS-months) [ITT]	11_4_1_1 FIG.RTF
12.1	Summary of exposure [ITT]	12_1_1.RTF
12.1	Route of administration and settings by patient [ITT]	12_1_2.RTF
12.1	Route of administration and settings by cycle [ITT]	12_1_3.RTF
12.1	Exposure: Description of cycles [ITT]	12_1_4.RTF
12.1	Exposure: Cumulative dose, actual dose intensity and relative dose intensity by patient [ITT]	12_1_5.RTF
12.1	Exposure: Actual dose intensity and relative dose intensity by cycle [ITT]	12_1_6.RTF
12.1	Dose delayed and reasons [ITT]	12_1_7a.RTF
12.1	Listing of the reasons of dose delayed [ITT]	12_1_7b.RTF
12.1	Dose reduction of Vinflunine and reasons [ITT]	12_1_8a.RTF
12.1	Reasons by dose reduction of Vinflunine [ITT]	12_1_8b.RTF
12.1	Listing of the reasons of Vinflunine dose reductions [ITT]	12_1_8c.RTF
12.1	Dose reduction of Methotrexate and reasons [ITT]	12_1_8d.RTF
12.1	Reasons by dose reduction of Methotrexate in VFL+MTX group [ITT]	12_1_8e.RTF
12.1	Reasons by dose reduction of Methotrexate in MTX group [ITT]	12_1_8f.RTF
12.1	Listing of the reasons of Methotrexate dose reductions [ITT]	12_1_8g.RTF
12.1	Methotrexate cancellations and reasons [ITT]	12_1_9a.RTF
12.1	Listing of the reasons of Methotrexate cancellations [ITT]	12_1_9b.RTF
12.1	Vinflunine cancellations and reasons [ITT]	12_1_9c.RTF
12.1	Listing of the reasons of Vinflunine cancellations [ITT]	12_1_9d.RTF
12.1	Treatment interruption and reasons [ITT]	12_1_10a.RTF
12.1	Listing of the reasons of treatment interruptions [ITT]	12_1_10b.RTF
12.1	Dose discontinuations of Vinflunine or Methotrexate [ITT]	12_1_11a.RTF
12.1	Listing of patients with discontinuation of VInflunine or Methotrexate [ITT]	12_1_11b.RTF
12.2.1	Summary of Adverse Events [Safety set]	12_2_1.RTF

SECTION	TITLE	RTF reference
12.2.2	Adverse events whatever their relationship to study drug – Worst grade events per patient by SOC and PT [Safety set]	12_2_2_1a.RTF
12.2.2	Adverse events whatever their relationship to study drug – Worst grade events per cycle by SOC and PT [Safety set]	12_2_2_1b.RTF
12.2.2	Drug-related adverse events – Worst grade events per patient by SOC and PT [Safety set]	12_2_2_1c.RTF
12.2.2	Drug-related adverse events – Worst grade events per cycle by SOC and PT [Safety set]	12_2_2_1d.RTF
12.2.2	AEOSI whatever their relationship to study drug – Worst grade events per patient by type [Safety set]	12_2_2_2a.RTF
12.2.2	AEOSI whatever their relationship to study drug – Worst grade events per type [Safety set]	12_2_2_2b.RTF
12.2.2	Drug-related AEOSI – Worst grade events per patient by type [Safety set]	12_2_2_2c.RTF
12.2.2	Drug-related AEOSI – Worst grade events per cycle by type [Safety set]	12_2_2_2d.RTF
12.2.2	Serious adverse events whatever their relationship to study drug – Worst grade events per patient by SOC and PT [Safety set]	12_2_2_3a.RTF
12.2.2	Drug-related Serious adverse events – Worst grade events per patient by SOC and PT [Safety set]	12_2_2_3b.RTF
12.2.2.4	Worst CTCAE grade of haematological parameters by patient [Safety set]	12_2_2_4_1a.RTF
12.2.2.4	Worst CTCAE grade of haematological parameters by cycle [Safety set]	12_2_2_4_1b.RTF
12.2.2.4	Shift table of Worst CTCAE grade by patient according to grade at baseline for haematological parameters [Safety set]	12_2_2_4_1c.RTF
12.2.2.4	Worst CTCAE grade of biochemical parameters by patient [Safety set]	12_2_2_4_2a.RTF
12.2.2.4	Worst CTCAE grade of biochemical parameters by cycle [Safety set]	12_2_2_4_2b.RTF
12.2.2.4	Shift table of Worst CTCAE grade by patient according to grade at baseline for biochemical parameters [Safety set]	12_2_2_4_2c.RTF
12.2.2.4	Worst CTCAE grade of SGOT/AST by patient according to the presence of liver metastases at baseline [Safety set]	12_2_2_4_2d.RTF
12.2.2.4	Worst CTCAE grade of SGPT/ALT by patient according to the presence of liver metastases at baseline [Safety set]	12_2_2_4_2e.RTF
12.2.2.4	Worst CTCAE grade of alkaline phosphatase by patient according to the presence of liver and/or bone metastases at baseline [Safety set]	12_2_2_4_2f.RTF
12.3.1.1	Summary of deaths [Safety set]	12_3_1_1a.RTF
12.3.1.1	Listing of dead patients within 30 days after last administration, reason of death, relationship to treatment [Safety set]	12_3_1_1b.RTF
12.3.1.1	Listing of dead patients within 30 days more than 30 days after last administration, reason of death, relationship to treatment [Safety set]	12_3_1_1c.RTF
12.3.1.2	Listing of Serious Adverse Events [Safety set]	12_3_1_2.RTF
14.1.1	Prior medications whatever the indication per patient at baseline [ITT]	14_1_1.RTF
14.1.2	Prior medications with a tumour related indication per patient at baseline [ITT]	14_1_2.RTF
14.1.3	Prior medications with a prophylactic indication per patient at baseline [ITT]	14_1_3.RTF
14.1.4	Prior medications with pre-treatment event indication per patient at baseline [ITT]	14_1_4.RTF
14.1.5	Prior medications with medical history indication per patient at baseline [ITT]	14_1_5.RTF
14.1.6	Prior medical history by patient according to MedDRA System Organ Class and Preferred Term [ITT]	14_1_6.RTF
14.1.7	Pre-treatment events by patient according to MedDRA System Organ Class and Preferred Term [ITT]	14_1_7.RTF
14.2	Progression-Free Survival (PFS-months) [ITT]	14_2_1.RTF
14.2	Progression-Free Survival (PFS-months) [ITT]	14_2_1 FIG.RTF
14.2	Objective Response Rate (ORR) [ITT]	14_2_2.RTF
14.2	Disease Control Rate (DCR) [ITT]	14_2_3.RTF

SECTION	TITLE	RTF reference
14.2	Duration Of Response (months) [ITT]	14_2_4.RTF
14.2	Duration Of Response (months) [ITT]	14_2_4 FIG.RTF
14.2	Duration of Disease Control (months) [ITT]	14_2_5.RTF
14.2	Duration of Disease Control (months) [ITT]	14_2_5 FIG.RTF
14.2	Time to Treatment Failure (months) [ITT]	14_2_6.RTF
14.2	Time to Treatment Failure (months) [ITT]	14_2_6 FIG.RTF
14.2	Time to First Response (months) [ITT]	14_2_7.RTF
14.2	Time to First Response (months) [ITT]	14_2_7 FIG.RTF
14.3	Electrocardiogram: listing of abnormalities at baseline [Safety Set]	14_3_1.RTF
14.3	Electrocardiogram: listing of abnormalities during treatment period [Safety Set]	14_3_2.RTF
14.4.1a	Concomitant medications whatever the indication per patient [ITT]	14_4_1a.RTF
14.4.1b	Concomitant medications whatever the indication per cycle [ITT]	14_4_1b.RTF
14.4.2a	Concomitant medications with a tumour related indication per patient [ITT]	14_4_2a.RTF
14.4.2b	Concomitant medications with a tumour related indication per cycle [ITT]	14_4_2b.RTF
14.4.3a	Concomitant medications with a prophylactic indication per patient [ITT]	14_4_3a.RTF
14.4.3b	Concomitant medications with a prophylactic indication per cycle [ITT]	14_4_3b.RTF
14.4.4a	Concomitant medications with pre-treatment event indication per patient [ITT]	14_4_4a.RTF
14.4.4b	Concomitant medications with pre-treatment event indication per cycle [ITT]	14_4_4b.RTF
14.4.5a	Concomitant medications with medical history indication per patient [ITT]	14_4_5a.RTF
14.4.5b	Concomitant medications with medical history indication per cycle [ITT]	14_4_5b.RTF
14.5	EORTC QLQ-C30 (Global Health Status) : Values and changes from baseline Over Time and at last cycle [Evaluable Pop for QLQ-C30]	14_5_1a.RTF
14.5	EORTC QLQ-C30 (Functional scales): Values and changes from baseline Over Time and at last cycle [Evaluable Pop for QLQ-C30]	14_5_1b.RTF
14.5	EORTC QLQ-C30 (Symptom Scales/Items) : Values and changes from baseline Over Time and at last cycle [Evaluable Pop for QLQ-C30]	14_5_1c.RTF
14.5	QLQ-Head and Neck EORTC 35 Module (Multi-item scales) : Values and changes from baseline Over Time and at last cycle [Evaluable Pop for QLQ-H&N 35]	14_5_2a.RTF
14.5	QLQ-Head and Neck EORTC 35 Module (Single items) : Values and changes from baseline Over Time and at last cycle [Evaluable Pop for QLQ-H&N 35]	14_5_2b.RTF
16.2.1	Discontinued patients	16_2_1_1.RTF
16.2.1	Follow-Up data	16_2_1_2.RTF
16.2.2	Protocol Deviations at study entry	16_2_2_1.RTF
16.2.2	Protocol Deviations on treatment	16_2_2_2.RTF
16.2.3	Analysis sets	16_2_3_1.RTF
16.2.3	Eligibility criteria	16_2_3_2.RTF
16.2.3	Randomization criteria	16_2_3_3.RTF
16.2.4	Patients' characteristics	16_2_4_1.RTF
16.2.4	Disease characteristics	16_2_4_2.RTF
16.2.4	Prior surgery for SCCHN	16_2_4_3a.RTF
16.2.4	Prior radiotherapy for SCCHN	16_2_4_3b.RTF
16.2.4	Prior chemotherapy for SCCHN	16_2_4_3c.RTF
16.2.4	Prior treatment for SCCHN	16_2_4_3d.RTF
16.2.4	Medical and Surgical History, Concomitant disease	16_2_4_4.RTF
16.2.4	Pre-treatment events	16_2_4_5.RTF
16.2.4	Blood and Platelet transfusion	16_2_4_6.RTF
16.2.5	Treatment administration of Vinflunine	16_2_5_1.RTF

SECTION	Title	RTF reference
16.2.5	Treatment administration of Methotrexate	16_2_5_2.RTF
16.2.5	Treatment modifications	16_2_5_3.RTF
16.2.5	Cumulative dose, dose intensity and relative dose intensity per arm and per cycle	16_2_5_4.RTF
16.2.6	Tumour assessments	16_2_6_1.RTF
16.2.6	Work-Up	16_2_6_2.RTF
16.2.6	Efficacy parameters (1/2)	16_2_6_3.RTF
16.2.6	Efficacy parameters (2/2)	16_2_6_4.RTF
16.2.7	Adverse Events by patient (Reported Term, Preferred Term and Dates)	16_2_7_1.RTF
16.2.7	Adverse Events by System Organ Class and Preferred Term	16_2_7_2.RTF
16.2.7	Drug-related Adverse Events by patient (Reported Term, Preferred Term and Dates)	16_2_7_3.RTF
16.2.7	Drug-related Adverse Events by System Organ Class and Preferred Term	16_2_7_4.RTF
16.2.7	Serious Adverse Events by patient (Reported Term, Preferred Term and Dates)	16_2_7_5.RTF
16.2.7	Serious Adverse Events by System Organ Class and Preferred Term	16_2_7_6.RTF
16.2.7	Patient deaths	16_2_7_7.RTF
16.2.8	Individual haematological laboratory measurements by patient - grades and values	16_2_8_1.RTF
16.2.8	Individual biochemical laboratory measurements by patient - grades and values	16_2_8_2.RTF
16.2.8	Blood products	16_2_8_3.RTF
16.2.8	Pregnancy test results	16_2_8_4.RTF
16.2.8	Tumour Markers	16_2_8_5.RTF
16.2.9	Temperature, vital signs, weight	16_2_9_1.RTF
16.2.9	Neurological examination, physical examination	16_2_9_2.RTF
16.2.9	ECG results	16_2_9_3.RTF
16.2.10	Prior and Concomitant medications	16_2_10_1.RTF
16.2.10	Concomitant Radiotherapy	16_2_10_2.RTF
16.2.10	Concomitant surgery	16_2_10_3.RTF
16_2_11	EORTC QLQ-C30	16_2_11_1_1.RTF
16_2_11	EORTC QLQ-C30, derived scores	16_2_11_1_2.RTF
16_2_11	QLQ Head & Neck 35 EORTC module	16_2_11_2_1.RTF
16_2_11	QLQ Head & Neck 35 EORTC module, multi-item scales	16_2_11_2_2.RTF

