4.2. EXCLUSION CRITERIA

If any of the following apply, the patient must not enter into the study:

1. Nasopharyngeal carcinoma
2. History of brain or leptomeningeal involvement
3. History of other cancers except other synchronous head and neck squamous cell carcinomas, adequately treated in situ carcinoma of the cervix uteri, basal or squamous cell carcinoma of the skin or other cancer curatively treated with surgery and/or radiotherapy (with or without other anti-cancer therapy) and with no evidence of disease for at least 3 years
4. Albumin level < 35 g/L
5. Patients with weight loss \geq 5% within the last 3 months

6. Recurrent pulmonary or upper airways infections (3 times or more in the last 3 months) requiring antibiotics and/or any infection requiring antibiotics within the last month before study entry
7. Grade ≥ 2 peripheral neuropathy at study entry according to NCI-CTC AE (version 3.0)
8. Serum potassium < the lower limit of normal
9. ECG demonstrating a QT/QTc interval > 480 msec
10. A female is not eligible to enter the study if :
 - . Pregnant or lactating
 - . With positive pregnancy test at inclusion
11. Female of childbearing potential who is unwilling or unable to use a medically accepted method to avoid pregnancy during the 2 months preceding the start of study treatment, throughout the study period and at least 3 months following the last dose of study treatment
Male unwilling or unable to use a medically accepted method to avoid pregnancy throughout the study period and at least 3 months following the last dose of study treatment if their partners are women of childbearing potential
12. Patients with any underlying medical condition that might be aggravated by treatment or which cannot be controlled i.e. active serious infection, poorly controlled diabetes mellitus, concurrent heart failure [New York Heart Association (NYHA) class III-IV] or with progressive or unstable angina, myocardial infarction within 6 months, and/or poorly controlled hypertension.
13. "Third space" fluids (pleural effusion, ascites, massive edema)
14. Concomitant treatment with any other anti-cancer therapy and contraindicated medication (see Section 6.1)
15. Prior treatment with vinca-alkaloids and methotrexate
16. Participation into a clinical study of an investigational agent within 30 days before study entry

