6.2. RESTRICTED TREATMENT

6.2.1. Arm A

Caution is warranted when administering vinflunine to patients taking drugs that are highly dependent on CYP3A4 for metabolism and have a narrow therapeutic index. Systemic exposure to these medications could be increased while receiving vinflunine.

Even if no data is available, the opposite impact to that from inhibitors (that is decrease in vinflunine blood levels) may be anticipated. Concomitant **CYP3A4 inducers** should be avoided (list provided in Appendix 8), if possible, since they could alter the systemic exposure to vinflunine.

The use of concomitant medications that prolong the QT/QTc interval should be avoided (list provided in <http://crediblemeds.org/everyone/composite-list-all-qtdrugs/?rf=All>).

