- Lesions on chest X-rays are acceptable as measurable lesions when they are clearly defined and surrounded by aerated lung.
- Ultrasound is not an acceptable method to measure disease.
- All adverse events which occurred during the cycle must be assessed and documented using the CTCAE version 3.0.
- ECG to be performed on day 1 of cycle 1 before and after drug administration in both arms. Thereafter, ECG will be performed before drug administration every 2 cycles in both arms. After review of safety data including ECG results by the IDMC, the need for repeated ECGs before each cycle can be revised. In case of QT/QTc > 500 msec (grade 3), patients should be hospitalized for a close and continuous ECG monitoring until cardiology consultation.
- Concurrent prescriptions, blood products, palliative radiotherapy must be documented.

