11.5.4. Safety assessment

11.5.4.1. Safety parameters

Haematological parameters (WBC, ANC, platelets, haemoglobin), febrile neutropenia, biochemical parameters (ALT, AST, alkaline phosphatase, creatinine, total bilirubin) and non haematological toxicities will be assessed. The NCI CTC AE version 3.0 will be used.

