### Clinical examination

Electrocardiogram (normal/abnormal but not clinically significant/abnormal clinically significant),

Baseline biological abnormalities,

Baseline haematological abnormalities.

Temperature, Blood Pressure, Pulse

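### On-treatment ECG, including QT/QTc, is only listed in the SAP, with no by-arm summary; QT prolongation is counted by arm only if reported as an adverse event

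*SAP*

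**What the plan says.** **Protocol, collection.** Section 7.4 sets the schedule: "ECG to be performed on day 1 of cycle 1 before and after drug administration in both arms", then before dosing every two cycles. Section 8.2.1 lists ECG among the clinical safety assessments and lets the IDMC's review of the results change the schedule.

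**Protocol, QT/QTc levels.** Section 4.2 excludes patients with "ECG demonstrating a QT/QTc interval > 480 msec". Section 6.2.1 adds for arm A: "The use of concomitant medications that prolong the QT/QTc interval should be avoided". Section 7.4 sets an on-study level: "In case of QT/QTc > 500 msec (grade 3), patients should be hospitalized for a close and continuous ECG monitoring until cardiology consultation".

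**Protocol, analysis.** Section 11.5.4.1 names the safety parameters, and ECG is not among them: "Haematological parameters (WBC, ANC, platelets, haemoglobin), febrile neutropenia, biochemical parameters (ALT, AST, alkaline phosphatase, creatinine, total bilirubin) and non haematological toxicities will be assessed".

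**SAP.** Sections 5 and 11 do not mention ECG. Section 9.1.2 summarises it at baseline only, in three categories: "Electrocardiogram (normal/abnormal but not clinically significant/abnormal clinically significant". Appendix 1 adds "Electrocardiogram: listing of abnormalities at baseline [Safety Set" (14.3.1), "Electrocardiogram: listing of abnormalities during treatment period [Safety Set" (14.3.2) and an individual ECG results listing (16.2.9.3).

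**The concern.** ECGs are taken in both randomised arms, with a pre-dose and a post-dose recording on the first treatment day. That design allows a comparison between arms. A listing has no denominator, no proportion and no change from baseline, so the reader of the study report would have to build the comparison by hand.

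The substitute is adverse event reporting. An ECG change without symptoms enters the AE tables only when an investigator records it as an AE. The trial is open-label, so the readiness to do so may differ by arm. A tabulated ECG category, and still more a tabulated interval, is less exposed to that.

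**Working it through.** The plan states no figure to reproduce. The check is a comparison of passages, followed by one illustration of precision.

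**1. Outputs for on-treatment data (SAP Appendix 1).**

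| Data | Listings | By-arm summary tables |
|---|---|---|
| Haematology | individual values and grades (16.2.8.1) | worst grade by patient, worst grade by cycle, shift from baseline |
| Biochemistry | individual values and grades (16.2.8.2) | the same three, plus three split by metastases at baseline |
| ECG | 14.3.2 and 16.2.9.3 | none |

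SAP 8.1 presents descriptive statistics by arm, so the laboratory tables are by-arm tables. The only by-arm ECG summary is the baseline one (SAP 9.1.2, table 11.2.11), before any drug effect could appear.

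**2. Does the move to an abbreviated report explain the gap?** SAP section 13 lists the analyses deleted under amendment 11, and no ECG summary is among them. The same section says that the safety description is to remain complete. Protocol 11.5.1 says that the safety analyses go ahead as planned.

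**3. The adverse event route.** SAP 11.1 to 11.2.3 tabulate treatment-emergent AEs and SAEs by arm, by system organ class, preferred term and worst grade. Four per-patient tables in Appendix 1 (12.2.2) could carry a reported QT event: all AEs, related AEs, all SAEs and related SAEs. Whether a measured prolongation reaches them is less certain:

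- Protocol 9.1.3 states when a haematology or biochemistry abnormality must also be entered as an AE. It has no such rule for ECG findings.
- Above 500 msec, the admission described in protocol 7.4 would meet the hospitalisation criterion for an SAE (9.2.1). However, the SAE form in Appendix 5 excepts hospitalisations foreseen by the protocol, so capture by this route is not settled.
- For on-treatment values from above 480 up to 500 msec, the documents give no reporting rule.
- The AEs of special interest include arrhythmias and conduction disorders (SAP 5.1.1, Appendix 3), but no QT term is named. Whether the listed MedDRA High Level Terms contain one cannot be decided from the documents.

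**4. What a table could show.** Inputs: 459 randomised, 230 in arm A and 229 in arm B (protocol synopsis), so n is at most about 230 per arm. The safety set is treated patients only, and the denominator would be those with an on-treatment ECG, so the true n is smaller. The rate p = 5% is an assumption, used for scale only.

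- One arm: 1.96 × √(p(1 − p)/n) = 1.96 × √(0.05 × 0.95/230) = 0.028, or ±2.8 points.
- Difference between arms: 1.96 × √(2p(1 − p)/n) = 1.96 × √(2 × 0.05 × 0.95/230) = 0.040, or ±4.0 points.

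The second figure is the relevant one for a comparison of arms.

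**The case against.** The strongest reply is that QT events are not lost. An AE is any unfavourable sign (protocol 9.1.1), AEs that are observed must be recorded (9.1.3), and the protocol itself grades a value above 500 msec. A reader might infer from the table list that QT prolongation will have no rate by arm at all. The documents do not support that, because a reported event is tabulated by arm. What remains is that the count depends on reporting.

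Second, a reader might infer that QT prolongation is an established vinflunine effect. The documents do not say so. Protocol Table 3 and the safety narrative after it do not mention QT, and the ECGs also serve other cardiac events. The exclusion, the medication restriction and the 500 msec level show a monitored risk, no more.

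Third, a reader might assume that QTc tables need only data already in hand. The one ECG variable that the SAP describes is a three-category interpretation; listing 16.2.9.3 is titled only as ECG results, and no correction formula is stated. QT/QTc values may not be in the eCRF. This objection stands and sets the order of the fix.

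Fourth, the pre- to post-dose change would be rough. No post-dose time is fixed, and the recording follows a 20-minute infusion plus methotrexate in arm A but a methotrexate bolus in arm B. This also stands, as a caution on interpretation.

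Finally, the IDMC sees ECG results, the trial stopped recruiting after a futility analysis, and protocol 11.5.4 never promised an ECG analysis. These points limit the weight of the concern. They do not put a by-arm summary into the study report.

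**Conclusion.** The point holds in this form: on-treatment ECG, including any QT/QTc values, is reported by listings alone, and a by-arm count of QT prolongation depends on unspecified AE reporting in an open-label trial. It is a gap in safety description with no bearing on overall survival, and it should be closed because the ECGs are already scheduled in both arms.

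The category comparison rests on two assumptions: that the three-category interpretation described for baseline was also recorded on treatment, and that most treated patients have at least one on-treatment ECG. Any QTc table further requires that the values were captured. The ±2.8 and ±4.0 points depend on the assumed 5% rate and the upper limit of about 230 per arm; with fewer evaluable patients both widen.

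**What to change.** Add the following to SAP section 11 and Appendix 1, for the safety set by arm, with patients who have at least one on-treatment ECG as the denominator:

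1. A shift table from baseline to worst on-treatment ECG category, using the three categories of SAP 9.1.2.
2. Where QT/QTc values are in the eCRF, the number and percentage of patients with worst on-treatment QTc ≤ 480, > 480 to 500 and > 500 msec. These are the protocol's own levels, used here only to describe the data. State how many patients have values.
3. Where values exist, the cycle 1 day 1 pre- to post-dose change (mean, SD, range), with a note that post-dose timing is not fixed and differs between arms.

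Name one QT correction and use it throughout, since the documents say only QT/QTc. Describe QT as a monitored risk.

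The cost is one to three descriptive tables and a paragraph of SAP text. No new assessment and no change to patient management is involved.
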